At the University of Pennsylvania, we see approximately 20 cases of extremity STS per year. We anticipate that with the availability of proton radiotherapy, these numbers may increase. We estimate an annual accrual of 12 subjects per year for each cohort. We will also treat patients either preoperatively or postoperatively from Walter Reed Army Medical Center. In addition, this protocol will be listed on our web site as a formal protocol and information of its availability will be made known to treating professionals throughout our satellites as well as other referring physicians. These patients, if treated preoperatively with radiation therapy, will be required to have their surgery at the Hospital of the University of Pennsylvania.

Early Withdrawal of Subjects

When and How to Withdraw Subjects?

Recurrent or Progressive Disease: Subjects who have clinical or radiologic evidence of recurrent disease will undergo an evaluation to document the nature of the abnormality. If recurrent or progressive cancer is diagnosed, the subject will be considered off study at that time.

Subject Participation: Subjects may be withdrawn if the subject decides to refuse continuation of treatment or follow-up. Subjects may also be withdrawn for non-compliance with the protocol or withdrawal of consent. The reasons for withdrawal will be documented.

PI Decision: Subjects may be withdrawn at any time during the study if the PI believes it is in the subject's best interest. In this event, the reasons for withdrawal will be documented.

Once the subject has discontinued treatment, the primary reason for discontinuing treatment must be clearly documented in the subject's records and on the CRF. The investigator will assess each subject for response at the time of withdrawal.

Every effort will be made to follow subjects off study for toxicity and survival. Survival will be followed for a minimum of 5 years by means of scheduled appointments and available medical records. Every effort will be made to follow for overall survival.

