Patient cannot be given treatment because anatomy is such that a dosimetrically satisfactory treatment plan cannot be devised. For example, the dosimetry is unsatisfactory if <95% of target volume is covered by 95% of the dose.

Patient is unable to tolerate 25% of treatments using proton radiotherapy, that is, up to 25% of treatments could be delivered using photons. Reasons for missed treatments may include: unable to set patient up within acceptable limits of tolerance, patient unable to tolerate treatment position or immobilization for duration of treatment).

Patient is unable to complete all of his/her treatments within 10 days of estimated date of treatment completion or requires a treatment break greater than 5 days.

(ii) **Acute toxicity** is defined as any grade 3 or higher hematologic or non-hematologic toxicity that is probably or definitely related to radiotherapy (not surgery). All toxicities observed within 90 days from start of radiotherapy, will be graded by NCI CTC Version 4.0. For pre-operative patients all toxicities observed within 90 days after start of radiation treatment or 30 days after surgery, whichever comes later, will be graded.

Secondary Endpoints:

(i) **Late toxicity** is defined as any grade 3 or higher hematologic or non-hematologic toxicity which occurs after 90 days from start of therapy. Late toxicities will be graded according to the RTOG/EORTC late toxicity criteria. The time frame for late toxicity is open-ended and late toxicities have been known to occur a year or more after therapy. Follow-up for late toxicity will cease when a patient experiences disease progression, since 2nd line therapies may then be initiated.

(ii) **Wound complication** is defined as a secondary operation under general or regional anesthesia for wound repair or wound management without second operation. Wound management includes an invasive procedure without general or regional anesthesia, readmission for wound care such as iv antibiotics, or persistent deep packing for 120 days or longer. Patients will be assessed for wound complications which develop within 4 months after surgery.

(iii) **Fibrosis and joint stiffness** will be graded according to EORTC/RTOG late radiation toxicity criteria. **Edema** will be graded as 0= none, 1= mild, 2= moderate, 3= severe, 4= very severe, according to the criteria of Stern (Stern TN. Clinical examination: a textbook. Year Book Medical

CONFIDENTIAL

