Publishers, 1964). Patients will be assessed for fibrosis, joint stiffness and edema within 2 years of completion of radiotherapy.

Clinical Efficacy is defined for pre-operative patients as overall response rate (CR + PR according to RECIST criteria) which is scored after radiation and before surgery. Progression-Free Survival is defined from first day of treatment to first documented failure, death due to any cause or last patient contact alive. Overall Survival is defined from first day of treatment until death due to any cause or last patient contact alive. Time to local failure, time to distant failure, PFS and OS will be calculated from first day of radiation in the pre-operative patients and calculated from day of surgery in the post-operative patients.

Rules for Early Termination for Feasibility, Acute Toxicity and Wound Complication:

Bayesian probability calculations will be employed to define rules of early termination and end of trial evaluation for feasibility and safety. The tables below indicate termination rules after groups of 3 patients have been treated. Hundreds of patients with certain types of cancer have undergone radiation therapy with protons. Thus, we will assume some "prior" feasibility and safety data for protons delivered at the standard radiation dose for our Bayesian calculations. We will assume prior information equivalent to that of 6 treated patients, which is commonly required to establish feasibility and safety in a standard 3+3 phase I trial design.

Feasibility – conducted separately for each stratum

We will assume a beta (5,1) prior, which is information equivalent to feasibility established in 5 of 6 treated patients. A feasibility rate > 90% is considered acceptable. If the number of patients deemed feasible is less than or equal to the number in the table below then termination will be considered as it is highly unlikely that the feasibility rate is > 90%, as noted by the Bayesian posterior probabilities.

Bayesian Rule for Feasibility				
Patients treated	3	6	9	12
Patients who are feasible	1	4	6	9
Posterior Prob[feasibility rate >90%]	0.0	0.0	0.0	0.0
Action	Terminate enrollment			

Acute Toxicity – conducted separately for each stratum * excludes wound complication *

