6.2 PHASE II STUDY

Design and Objectives:

This stratified phase II trial is designed to evaluate early complications (e.g., wound complication in pre-operative patients) and late complications (e.g., fibrosis, joint stiffness and edema in post-operative patients). Patients with STS of the lower extremity only will be treated in the phase II study. Justification for enrolling lower extremity STS in phase II is that 80% of STS patients treated in the Department of Radiation Oncology have lower extremity STS and they are the subgroup who may benefit most from protons. For example in the study by O’Sullivan et al (Lancet 359, 2002), in pre-operative patients, the wound complication rate from photon radiotherapy in patients with lower extremity STS was 43% (30 events in 70 patients) compared to 5.5% (1 event in 18 patients) in upper extremity STS. 40 evaluable patients (including evaluable patients from the feasibility stage) will be enrolled in each stratum.

Endpoints:

Same endpoints as in Section 6.1: Wound complication, Fibrosis and joint stiffness, Edema, Acute toxicity, Late toxicity and Clinical Efficacy.

Evaluable for analysis:

For pre-operative patients, patients must have a minimum of 4 months of follow-up post-surgery to be evaluable and included in the phase II analysis. For post-operative patients, patients must have a minimum of 2 years of follow-up from the end of radiotherapy to be evaluable and included in the phase II analysis.

Rules for Early Termination for Wound Complications:

We will assume a beta (2,4) prior, which is information equivalent to wound complication in 2 of 6 treated patients. A wound complication rate >40% is considered unacceptable. If the number of patients with wound complications is greater than or equal to the number in the table below then termination will be considered as it is likely that the wound complication rate is >40%, as noted by the Bayesian posterior probabilities.

Bayesian Rule for Wound complication						
Patients treated & followed 4 months	1	2	2	3	3	4
Patients who experience wound complication	5	0	5	0	5	0
Posterior Prob[wound complication toxicity rate >40%]	8	1	1	1	1	1
		1	3	5	7	9
	0	0	0	0.	0.	0.
	.	.	.	8	7	7
	7	8	8	1	9	8
	6	5	2			
Action	Terminate enrollment					

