With 12 patients per year enrolled to each stratum and accounting for required follow-up time for feasibility and toxicities, this study should be active for 7 years. Twelve pre-operative and 12 post-operative patients will be enrolled on the feasibility portion of the trial. If feasibility and safety are acceptable then 40 evaluable pre-operative patients and 40 evaluable post-operative patients with STS of the lower extremity (each group includes evaluable patients from the feasibility stage) will be enrolled in the phase II portion of the trial. Up to 50 pre-operative patients may need to be enrolled to yield 40 evaluable patients with lower extremity STS who undergo surgery and have 4 months of follow-up post-surgery. With 40 evaluable patients, there will be 84% power for a chi-square test at one-sided 5% type I error to test a grade 2 or higher wound complication rate of 45% versus an alternative rate of 25%.

Similarly, up to 50 post-operative patients may need to be enrolled to yield 40 evaluable patients with lower extremity STS who receive post-operative radiotherapy and remain on-study for 2 years from the end of radiotherapy. With 40 evaluable patients, there will be 83% power for a chi-square test at one-sided 5% type I error to test a grade 2 or higher fibrosis rate of 50% versus an alternative rate of 30%. In addition, there will be 80% power for chi-square tests at one-sided 2.5% type I error to test grade 2 or higher joint stiffness and

CONFIDENTIAL

edema, each with rates of 25% versus alternative rates of 9%. These secondary analyses will be tested at a 2.5% significance level, to control the overall type I error.

All correlative analyses of hypoxia and clinical outcome are exploratory. Results from this unique study will be used to estimate the magnitude of the associations for both RECIST response and time-to-event outcomes and will provide important guidance for future studies of the prognostic importance of hypoxia in STS patients.

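### The plan gives conflicting rules on whether post-operative patients who progress before 2 years enter the primary fibrosis analysis

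*Combined protocol and SAP*

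**What the plan says.** **Status at progression.** Section 2 (Early Withdrawal of Subjects) states: "If recurrent or progressive cancer is diagnosed, the subject will be considered off study at that time". The same part then promises: "Every effort will be made to follow subjects off study for toxicity and survival".

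**Late-toxicity follow-up.** Section 6.1, secondary endpoint (i), defines late toxicity as grade 3 or higher events beyond 90 days from the start of therapy, and adds: "Follow-up for late toxicity will cease when a patient experiences disease progression, since 2nd line therapies may then be initiated".

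**Fibrosis.** This is a separate item, (iii), in the same list. Fibrosis and joint stiffness "will be graded according to EORTC/RTOG late radiation toxicity criteria", and the window is given as: "Patients will be assessed for fibrosis, joint stiffness and edema within 2 years of completion of radiotherapy". Item (iii) does not mention progression. Section 6.2 carries both items into Phase II as distinct endpoints: "Same endpoints as in Section 6.1: Wound complication, Fibrosis and joint stiffness, Edema, Acute toxicity, Late toxicity and Clinical Efficacy". Section 6.3 makes grade 2+ fibrosis the primary post-operative endpoint, tested one-sided at 5% against a null of 50%.

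**Evaluability.** Section 6.2 says "patients must have a minimum of 2 years of follow-up from the end of radiotherapy to be evaluable and included in the phase II analysis". The opening of Section 2 says the same in substance. Section 6.3 also asks for 2 years of follow-up, though counted from surgery. Only Section 6.4, in the sample-size paragraph, speaks of patients who "remain on-study for 2 years from the end of radiotherapy".

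**The concern.** A patient whose disease progresses at, say, 14 months is off study under Section 2 and so fails the on-study condition in Section 6.4. The same patient, seen off study until 2 years, meets the follow-up condition in Sections 2, 6.2 and 6.3. The two readings give different analysis sets for a primary endpoint, and nothing in the plan ranks them. Nor does it say what happens to a patient who already has grade 2+ fibrosis on record when progression is found. Under Section 6.4 that event disappears.

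The stake is selection on something that happens after treatment. The stratum has no concurrent control in which the same selection would occur; its rate is set against a fixed number. If progressors are left out, the estimate describes only patients free of progression at 2 years. If limb scoring also stops at progression, the effect of leaving them out cannot be fully examined afterwards.

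**Working it through.** **1. The plan's own power figure.** Inputs from Section 6.4: n = 40, null 50%, alternative 30%, one-sided 5%. One-sample normal approximation:

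power = Φ[(|p0 − p1| − 1.645·√(p0(1−p0)/n)) / √(p1(1−p1)/n)]
= Φ[(0.20 − 1.645 × 0.0791) / 0.0725] = 83.3%.

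The stated 83% reproduces. It is conditional on 40 evaluable patients, so it stands whichever analysis set is meant. The enrolment allowance is also consistent: 40/(1 − 0.20) = 50.

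**2. The readings side by side, for a patient who progresses before 2 years.**

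| Passages followed | In the fibrosis analysis? |
|---|---|
| Section 2 (off study at progression) + Section 6.4 (on-study for 2 years) | No, even with grade 2+ fibrosis recorded |
| Section 2 (off-study toxicity follow-up) + evaluability in Sections 2, 6.2, 6.3 | Yes, if seen to 2 years |
| Section 6.1 (i), if read as covering fibrosis | No scores after progression; treatment of earlier scores not stated |

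The first row does not depend on Section 6.1. Deleting that sentence would leave the exclusion in place.

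**3. Rejection cut-offs of the planned test (null 50%, one-sided 5%).**
- n = 40: 20 − 1.645 × √(40 × 0.25) = 20 − 1.645 × 3.162 = 14.8, so reject at 14 or fewer.
- n = 50: 25 − 1.645 × √(50 × 0.25) = 25 − 1.645 × 3.536 = 19.2, so reject at 19 or fewer.

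**4. Outer bound.** Assume that all 10 of the patients allowed for as non-evaluable (50 − 40) were progressors.
- Design result of 12/40 (30%): over all 50 the rate lies between 12/50 = 24% and 22/50 = 44%. Rejection is lost when 12 + k ≥ 20, that is, k ≥ 8 of the 10.
- Boundary result of 14/40: rejection is lost when 14 + k ≥ 20, that is, k ≥ 6 of the 10.
- If the 10 had the same 30% rate, the total is 15/50, which still rejects.

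**5. Direction.** Take illustrative rates that are not in the documents: 40% fibrosis in non-progressors and 20% of patients progressing. If fibrosis in progressors is 10%, the all-patient rate is 0.8 × 0.40 + 0.2 × 0.10 = 34%. If it is 50%, the rate is 0.8 × 0.40 + 0.2 × 0.50 = 42%. Against 40% with progressors excluded, exclusion can overstate or understate the rate.

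**The case against.** The best defence is that the plan's formal definitions already answer the question. The paragraph headed as the definition of evaluability in Section 6.2, and the opening of Section 2, rest on follow-up alone. The on-study phrase appears once, in a sample-size paragraph, and may be loose wording. This has force, and it shows which way the text is most easily reconciled. It does not remove the conflict, because the on-study phrase describes the 40 patients on whom the primary test is powered, and Section 2 gives off study a definite meaning.

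A reader might infer more: that Section 6.1 leaves every early progressor without a fibrosis score. The documents do not support that. The stop sentence sits under late toxicity, a grade 3+ endpoint with an open-ended time frame, whereas fibrosis has its own item and a fixed window. Grade 3+ fibrosis after 90 days does fit the literal late-toxicity definition, so the sentence may touch part of the endpoint, but the plan does not say so. In addition, the Section 5 schedule has toxicity assessed every 3 months for 2 years, so scores made before progression would exist. Only later ones are in doubt.

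A reader might also take the figures of 8 or 6 out of 10 as a likely reversal. They are not. The allowance of 10 covers every reason for non-evaluability. If the 50 include feasibility patients, some will have upper-extremity tumours and be excluded under any rule. At 12/40, reversal needs 80% fibrosis among those left out, against 30% in those analysed, and nothing in the plan suggests such a gap. The denominator behind the historical 48% in Section 6.3 is not given either, so a like-for-like restriction in that study cannot be ruled out.

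Finally, Section 6.1 gives possible second-line therapy as its reason for stopping. Whether that reason is sound for limb effects after distant progression is a clinical question that the documents do not settle, and this point does not rest on it.

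**Conclusion.** The contradiction stands. For the primary post-operative endpoint, the analysis set depends on which section is followed, and the reading through Sections 2 and 6.4 removes patients because of a post-treatment event even when the endpoint has already occurred. Section 6.1 adds to the conflict but is not its main source.

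The size and direction of any bias are unknown, because no progression rate and no fibrosis rate in progressors are given. The range of 24% to 44% at 12/40, with reversal only at 8 or more of 10 (6 or more at 14/40), is an outer bound that assumes every allowed non-evaluable patient progressed. The documents do not support a claim that the trial's conclusion would be biased in favour of protons, or that the sample size or power is wrong. The matter should be corrected before the analysis, since it decides who is counted.

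**What to change.** - Reconcile the withdrawal text in Section 2, the stop sentence in Section 6.1 and the on-study condition in Section 6.4 with the evaluability definitions in Sections 2, 6.2 and 6.3. In Section 6.4, replace the on-study condition with the follow-up-based definition, using one starting point for the 2 years throughout.
- State whether the Section 6.1 sentence applies to item (iii). State that the off-study toxicity follow-up promised in Section 2 includes fibrosis, stiffness and edema scores, with the date of progression and any later therapy recorded. Any clinical rule for when scoring should end is for the sponsor to set.
- Count grade 2+ fibrosis recorded before progression as an event. Say also how a patient counts who progresses without it and is not seen to 2 years, since counting only the events from this group would push the rate up.
- Add a sensitivity analysis in all treated lower-extremity post-operative patients: for example, cumulative incidence of grade 2+ fibrosis with death and local recurrence as competing events, or best-case and worst-case bounds.

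The cost is mainly wording. Toxicity visits every 3 months for 2 years are already scheduled in Section 5, and off-study toxicity follow-up is already promised. Some progressed patients will still miss visits, and later therapy may make attribution harder; recording that therapy allows this to be examined.

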There will be 2 cohorts of patients: (1) extremity STS patients undergoing pre-operative radiotherapy and (2) extremity STS patients undergoing post-operative radiotherapy. There will be two phases of this study. In the first part of the study, the feasibility and safety (as defined below) of proton therapy will be evaluated in 12 patients within each cohort. In this feasibility study, patients with STS of either the upper or lower extremity will be evaluated. If proton radiotherapy is found to be feasible and safe, the study will proceed to Phase II. Since a majority (80%) of patients seen in the Department will have lower extremity STS and complication rates are high in this subgroup, we will restrict enrollment to STS of the lower extremity in the Phase II study. In Phase II (for the pre-operative group), we will evaluate the risk of wound complications within 4 months of surgery compared to historical data from the randomized clinical trial described above¹⁹. In Phase II (for the post-operative group), we will evaluate the functional outcome (e.g., fibrosis, joint stiffness, edema) of patients at two years after the completion of therapy compared to historical data from the randomized clinical trial described above¹⁹.

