5 STUDY PROCEDURES

	Pre-treat	Day of F18-EF5 PET/CT Prior to injection	Weekly during RT	Visit prior to surgery	30 days post surg/RT ^{1*}	Q3 months for 2 years, then q6 months for years 3 - 5 after surgery/RT	Yearly (as long as the patient wishes to be followed)
Tests and Observations							
History and PE	X		X	X	X	X	X
ECOG PS	X						
Biopsy	X						
Urine Pregnancy Test		X ²					
Toxicity Assessment	X		X			X	
Tumor Measurement	X ¹			X		X	
18F-EF5 PET Scan (optional)	X ³						

1- *Post radiation/surgery follow-up schedule defined for each cohort in Section 6.

2- Urine pregnancy test is routinely performed prior to PET/CT scanning as departmental standard.

3 – Subjects may participate in study with or without performing 18F EF5 PET scan. This is a subject option.

Post-treatment Evaluation and follow-up

All subjects will be evaluated prior to initiation of treatment and weekly during the course of radiotherapy. For patients receiving pre-operative radiation, a visit will occur prior to surgery. This visit will involve an interval history and physical. All patients will be seen for a first post-operative/post-radiation office visit with either the attending radiation oncologist or surgeon no more than 30 days following surgery/radiotherapy or discharge from the hospital, whichever comes later. Pre-operative patients will be seen after surgery, weekly x 1 month, then every 2nd week x 1 month, then monthly for 3 months. Post-operative patients will be seen one month after surgery and then in 3 months. Follow up visits for pre-operative and post-operative patients will be with either the attending surgeon or radiation oncologist every 3 months for two years, and every 6 months thereafter for 3 years. These office follow-up visits will consist of an interval history and physical and imaging studies as clinically indicated. The wound complication endpoint will be scored at 4 months after surgery in the pre-operative group. Post-operative patients will be scored for fibrosis, edema and joint stiffness within 2 years after after radiation.

Assessment of Tumor Response

Tumor Response (RECIST criteria): RECIST criteria will only be evaluated after radiation just prior to surgery in the pre-operative patients. Post-operative patients will not be evaluated since they undergo complete resection of STS.

Target Lesions:

- **Complete Response (CR):** Disappearance of all target lesions.

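### Wound complication is scored at 4 months, but its packing component needs 120 days, so sections 5 and 6.1 must say how packing still in progress at scoring is counted

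*Combined protocol and SAP*

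**What the plan says.** The definition is in section 6.1, Endpoints, and section 6.2 carries it unchanged into Phase II. A wound complication is either a second operation under general or regional anesthesia for wound repair, or wound management without one. On the second route, "Wound management includes an invasive procedure without general or regional anesthesia, readmission for wound care such as iv antibiotics" and, as a further alternative, "persistent deep packing for 120 days or longer" all qualify. The same paragraph sets the window: "Patients will be assessed for wound complications which develop within 4 months after surgery".

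Section 5, under post-treatment evaluation, gives a scoring time: "The wound complication endpoint will be scored at 4 months after surgery in the pre-operative group". Section 6.2 adds that "patients must have a minimum of 4 months of follow-up post-surgery to be evaluable". Both wound stopping tables, in 6.1 and 6.2, also count patients with 4 months of follow-up.

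The visit schedule in section 5 runs beyond that point. After surgery, pre-operative patients are seen "weekly x 1 month, then every 2nd week x 1 month, then monthly for 3 months", which reaches about month 5. Visits are also planned every 3 months for two years.

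Wound complication is the Phase II primary endpoint in the pre-operative group (section 1) and the only event with a Phase II stopping table (section 6.2). Section 6.3 tests it against a null of 45%. The stopping rule treats a rate above 40% as unacceptable.

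**The concern.** One component of the endpoint takes at least 120 days to complete, and the endpoint is scored about 120 days after surgery. A wound that opens and is packed from week 3 (day 21) would meet the packing criterion only on about day 141, after the scoring date. No section says how packing still in progress at 4 months is recorded, or whether scoring waits for it. Two assessors could score the same patient differently.

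Any case left uncounted moves the observed rate down. Against the 40% stopping limit, that makes the safety rule slower to react. Against the fixed 45% null, it could help protons, depending on how the historical rate was counted.

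**Working it through.** **The plan's own figure.** Section 6.4 states 84% power for 40 evaluable patients, 45% versus 25%, one-sided 5%. The one-sample score test gives

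Φ[(0.45 − 0.25 − 1.645·√(0.45·0.55/40)) / √(0.25·0.75/40)] = Φ[(0.20 − 1.645·0.0787)/0.0685] = 84.9%.

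The exact binomial calculation gives 82.1%. The stated power is reproduced within 2 points and is not in dispute.

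**The rejection cut-off.** With 12 events in 40, z = (0.300 − 0.45)/0.0787 = −1.91, which rejects. With 13 events, z = (0.325 − 0.45)/0.0787 = −1.59, which does not. The test therefore claims benefit at 12 or fewer events. The exact type I error is P(X ≤ 12 | 40, 0.45) = 3.9%.

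**The date arithmetic.** Four calendar months last 120 to 123 days, depending on the start date (121.75 on average). The latest start of packing that reaches 120 days by the scoring date is 120 − 120 = 0 to 123 − 120 = 3 days after surgery.

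**Illustration for the 45% test.** The documents give no share of complications that qualify by packing alone, so 5% and 10% are assumptions. The calculation also assumes that the true rate is 45% and that the historical rate behind the null counts late-qualifying packing in full.

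| Share of complications missed | Observed rate | P(X ≤ 12 of 40) |
|---|---|---|
| none | 0.45 | 3.9% |
| 5% | 0.45 × 0.95 = 0.4275 | 6.9% |
| 10% | 0.45 × 0.90 = 0.405 | 11.6% |

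In absolute terms, losing 1 percentage point of the 45% gives 5.0%, and losing 5 points gives 12.9%. Each missed patient moves the observed rate by 1/40 = 2.5 points.

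**Illustration for the Phase II stopping rule.** The table in 6.2 is broken in the text available. Read as 8/15, 11/20, 13/25, 15/30, 17/35 and 19/40, its bounds give posterior probabilities of 0.76, 0.85, 0.82, 0.81, 0.79 and 0.78 under the beta(2,4) prior, which match the printed values. At a true complication rate of 50%, the chance of reaching a bound at some look is 78%. If 5% of complications are missed (observed rate 0.475) it is 68%, and if 10% are missed (0.45) it is 57%. This part does not depend on the historical definition, because the 40% limit is stated as an absolute rate.

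**The case against.** Three stronger readings are tempting, and the documents support none of them.

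First, a reader might infer that all patients with long packing are lost. They are not. Anyone who also has a second operation, an invasive procedure without general or regional anesthesia, or a readmission for wound care within the window counts on that ground. Only packing-alone cases are exposed.

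Second, a reader might infer that those cases are certain to be missed. That requires taking the scoring sentence in section 5 as a fixed date. The wording in 6.1 speaks of complications that develop within 4 months, which can be read as a limit on onset, with duration confirmed later. The 4 months for evaluability is a minimum. At 12 patients a year per cohort, most of the 40 will have been followed well beyond it by the final test, so the data would usually exist. This stands as a possible reading, but the plan does not adopt it and section 5 points the other way.

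Third, a reader might infer that the type I error of the primary test is inflated. The documents do not give the historical trial's wound definition or scoring time. The Introduction says only that "we will evaluate the risk of wound complications within 4 months of surgery compared to historical data from the randomized clinical trial". If that trial used the same criterion and cut-off, both rates are undercounted alike and the comparison with 45% is little affected. In that case, scoring the proton patients later would itself bias the comparison against protons. This objection stands, and it is why the figures for the 45% test are conditional. It does not remove the scoring ambiguity or the effect on the 40% limit.

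**Conclusion.** Sections 5 and 6.1 conflict, and nothing elsewhere in the plan resolves it. Followed literally, the packing component can be met only by packing that starts within 0 to 3 days of surgery. The conflict affects the pre-operative primary endpoint and its stopping rule, but only through patients who qualify by packing alone. Their number cannot be obtained from the documents.

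If such patients go uncounted, the rate is understated against the 40% limit. A bias towards protons in the 45% test needs the further condition that the historical rate counted them in full. The rise from 3.9% to 6.9% or 11.6% illustrates the size under that condition and an assumed share. It does not estimate what will happen in this trial. The point should be corrected, but it does not invalidate the design.

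**What to change.** Reconcile sections 5, 6.1 and 6.2 with four statements:

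- The 4-month limit applies to the onset of packing. Packing begun within 4 months is recorded at the visits already scheduled until it ends or reaches 120 days, and is then scored.
- The rate is reported twice: as scored at 4 months, and with late-qualifying packing cases added.
- The test against 45% uses whichever version matches the historical definition and window. This is settled from the historical source and written down before the analysis.
- At each stopping look, packing still in progress is handled by a stated rule, for example by showing the event count with and without pending cases.

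The definition itself does not change and no visit is added. The cost is later final scoring for a few packing-only patients. Packing begun at the end of month 4 (day 120 to 123) reaches 120 days at day 240 to 243, about month 8. Visits every 3 months date the end of packing only coarsely, so the start and stop dates should be recorded. The evaluability wording in sections 2, 6.2 and 6.3 and the stopping-table wording in 6.1 and 6.2 each need a matching sentence.
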